## **Abstract**

**Background:** Shoulder pain is one of the most common musculoskeletal complaints in orthopedic practice. Rotator cuff injuries account for up to 70% of pain in the shoulder girdle. There is no clinical study carried out in Brazil comparing cost effectiveness between the open and arthroscopic methods of rotator cuff repair surgery. **Purpose:** to determine which method of repair of the rotator cuff, open or arthroscopic, has the best cost effectiveness ratio. **Methods:** a randomized clinical trial will be carried out in which patients with symptomatic rotator cuff lesion will be submitted to repair surgery by either open or arthroscopic technique and will be subsequently evaluated. **Inclusion criteria:** a) patients with complete or incomplete high-grade rotator cuff lesion whose previous treatment failed or who did not tolerate non-surgical treatment; b) patients in good clinical condition to undergo surgery; c) clear understanding of the Portuguese language and accepting to participate in the study by signing the informed consent form. **Exclusion Criteria:** patients with previous shoulder surgery; b) limited range of motion of the shoulder (joint stiffness); c) previous fractures in the affected shoulder; d) signs of glenohumeral osteoarthritis; e) neurological injury; f) patients who opt not to participate and / or are not willing to sign the informed consent form; g) patients unable to complete the follow-up evaluation (inability to read or complete the forms). The sample size was calculated with safety margin and is 50 patients per group. All randomized patients will be monitored preoperatively and at 6, 24 and 48 weeks postoperatively for clinical outcomes (Constant-Murley and EuroQol-5D-3L) along with pain assessment (VAS). The Pearson's chi-square test or Fisher exact tests will be used to analyze the results of the two groups in relation to the categorical variables and for the inferential analysis of the numerical clinical outcomes, mixed models will be used and, if the normal distribution is not adequate, generalized mixed models will be used. The significance level of 5% ( $\alpha = 0.05$ ) will be used for all statistical tests, such that tests have a value of less than 0.05 will be considered statistically significant. Cost effectiveness analysis will also be performed, with Utilities calculations, quality adjusted life years (QALY), and incremental cost effectiveness ratio (ICSI).

Keywords: rotator cuff; surgery; arthroscopy; open repair; cost-effectiveness; QALY

## Introduction

Musculoskeletal injuries are a major cost to the healthcare system. In 2004, 30% of the North American population had some kind of musculoskeletal disorder that required medical treatment; between 2002 and 2004, the estimated cost of treating these changes was \$ 510 billion. Shoulder diseases represent the third most common cause of these changes, behind only spinal and knee disorders. (referências)

An evaluation of the primary health care system in Cambridge, United Kingdom, showed that the average frequency of shoulder pain was 9.5 per 1,000 individuals. Of these, 86% had rotator cuff tendinopathy. North American data estimate that approximately 4.5 million patients annually seek medical attention due to shoulder pain; of these, two million have some symptoms related to the rotator cuff. About 250,000 rotator cuff repair surgeries are performed annually in the United States of America (US), and with the continued increase in life expectancy and aging, there is a tendency to increase this number. (ref)

The rotator cuff is composed of the tendons of the subscapularis, supraspinatus, infraspinatus and teres minor muscles. The long portion of the biceps tendon also contributes to cuff function, which is to stabilize the humeral head in the glenoid cavity, preventing superior migration of the humeral head. (ref)

The possible lesions range from tendon degeneration (tendinosis / tendinopathy), through partial lesions (articular, interstitial or bursal), to complete lesions. Diagnosis is made by associating history and physical examination along with imaging methods, and magnetic resonance imaging (MRI) is considered the method of choice. (ref)

Currently the indication for surgical treatment is based on the persistence of symptoms and / or the degree of muscle weakness and / or size of the lesion, after a time of conservative treatment. In general, when opting for surgery, imaging can assist in the planning of surgical treatment, since it allows measuring the extent of the lesion (partial or total) and discriminating which tendons are involved (supraspinatus, infraspinatus, etc.).

Treatment of rotator cuff diseases depends on the type of injury, the patient's degree of activity, age, and the presence of symptoms. In general, tendon degeneration and partial lesions are treated non-surgically, with physiotherapy, infiltrations and analgesic medications. Complete and incomplete lesions that did not respond well to

conservative treatment, however, should be treated surgically. (ref)  
Among the surgical options, the open method is still considered the gold standard, with good or excellent results in over 90% of cases (ref). With the advent of arthroscopy and the evolution of arthroscopic instruments and implants in the last decade, the arthroscopic repair technique has gained space and is widely used in our country. Several studies abroad (REF) did not demonstrate superiority of one technique over another in terms of clinical outcomes. As the cost of arthroscopic surgery is higher, due to the equipment needed to perform it, it is important to establish which option has the best cost-effectiveness.

Some studies abroad (REF) even suggest the superiority of the open method over the arthroscopic method. However, there are no studies comparing cost-effectiveness between open and arthroscopic methods in Brazil. Therefore, the aim of the present study is to compare the open and arthroscopic methods for rotator cuff repair and determine which presents the best cost-effectiveness ratio.

This project will be submitted to FAPESP for research grant request in order to register it in TRIALS.GOV, as well for its publication and the acquisition of part of the surgical material (fixation anchors).

## **Hypothesis**

The hypothesis of this study is that the open method of rotator cuff repair will be more cost-effective compared to the arthroscopic method.

## **Justification**

In a systematic literature search, it was observed that there are no studies in the Brazilian literature comparing the cost-effectiveness of open and arthroscopic rotator cuff repair methods. Data from the international literature (REF) suggest that the open repair method is more cost-effective than the arthroscopic method (same clinical outcome and lower cost).

Thus, despite the high incidence of rotator cuff injury, there is insufficient evidence from the Brazilian experience to determine the best method for treating these injuries. So, this project proposes to conduct a study to answer the clinical question of which method, open or

arthroscopic, has the best cost-effectiveness in the surgical treatment of rotator cuff injury. According to the levels of scientific evidence, the most appropriate study design to answer this clinical question is a randomized clinical trial (Figure 1).

### **Study Goal**

The aim of the present study is to compare the open and arthroscopic methods for rotator cuff repair and determine which presents the best cost-effectiveness ratio.

### **Methodology**

#### **Study Design**

This project will be a multicenter randomized clinical trial and has a 33 month schedule, where 1 month will be the period for organizing the structure in which patients will be seen, followed by 18 months of recruitment, 12 months for follow-up of outcomes, and 02 months for analysis of the results. The study will be conducted at Hospital Alvorada Moema (Shoulder and Elbow Surgery Center of Excellence), Sao Paulo, Brazil, in conjunction with the Israeli Institute of Teaching and Research at Albert Einstein Hospital, Sao Paulo, Brazil, and D Municipal Hospital [name] (M'Boi Mirim) between August / 2019 and December / 2021. This project will be submitted to FAPESP for research grant request in order to register it in TRIALS.GOV, as well for its publication and the acquisition of part of the surgical material (fixation anchors).

This study will be submitted to the research ethics committee of Albert Einstein Hospital, Alvorada Moema Hospital and [name] Municipal Hospital (M'Boi Mirim).

In order to ensure methodological quality in this project, we will follow the guidelines and flowchart (Figure 2) recommended by the Consolidated Standards of Reporting Trials (CONSORT Statement), which are: adequate randomization, sample calculation, description and justification for losses, use of the intention-to-treat principle and appropriate follow-up time (REF).

## **Participants**

Patients participating in the study will be recruited and evaluated at the Shoulder and Elbow Surgery Center of Excellence at Alvorada Moema Hospital, a referral center for the treatment of shoulder and elbow injuries, and at [name] Municipal Hospital (M'Boi Mirim). Both hospitals will be co-participants in the project in question. Patients will undergo clinical evaluation, plain radiography and magnetic resonance imaging to confirm the diagnosis of rotator cuff injury. At this moment, the type of lesion will be evaluated, as well as its size, retraction (REF) and the degree of fatty infiltration of the muscular belly, according to the Goutallier classification (REF). The lesions will be classified as small (<1cm); moderate (1-3cm); large (3-5cm) or very large (> 5cm) (30). All patients will undergo examinations and preoperative clinical evaluation.

## **Inclusion Criteria**

- Patients over 18 years old
- Patients with complete rotator cuff injury, symptomatic, where there was failure or the patient could not support the non-surgical treatment;
- Patients with high-grade partial rotator cuff injury where therapy failed or the patient did not support non-surgical treatment;
- Patients without medical contraindications for surgery
- Patients with good understanding of Portuguese language and who agree to participate and sign the Informed Consent Form.

## **Exclusion Criteria**

- Patients under 18 years old
- Patients with previous shoulder surgery,
- Passive range of motion limitation (joint stiffness),
- Previous fractures
- Signs of glenohumeral osteoarthritis
- neurological injury
- Patients who choose not to participate and / or who do not accept to sign the consent form.

## **Allocation and Randomization**

After eligibility assessment, all patients will be informed about the nature and purpose of the study and will only be included in the randomized distribution after signing the informed consent form. Patients will be consecutively allocated to one of two proposed treatment methods: open rotator cuff repair or arthroscopic rotator cuff repair. Allocation will be made according to instructions contained in opaque and sealed envelopes that will be numbered according to the computer generated randomization list (<http://www.randomizer.org>). The sealed, opaque envelope containing the method to be applied will be attached to the patient record. A person not associated with the study will open the envelope before the intervention and after the anesthetic technique is applied.

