## **Team**

Five surgeons with at least 03 years of surgical technique experience will participate of this study: [name] [name], group leader and specialist in shoulder and elbow surgery since 1983; [name] [name], medical doctor graduated from UNICAMP/Sao Paulo (State University os Campinas) in 1999, with a residency in Orthopedics and Traumatology from UNIFESP (Federal University of Sao Paulo) in 2003 and specialist in shoulder and elbow surgery from Santa Casa de São Paulo in 2005; [name], medical

doctor graduated from UNIFESP (Federal University of Sao Paulo) in 2008, residency in Orthopedics and Traumatology from UNIFESP between 2009 and 2012, specialist in shoulder and elbow surgery from UNIFESP in 2013; [name] [name], medical doctor from USP (State University of Sao Paulo) between 2008 and 2013, residency in Orthopedics and Traumatology from USP between 2010 and 2013, specialized in shoulder and elbow surgery from USP in 2014; [name], medical doctor graduated from USP in 2011, residency in Orthopedics and Traumatology from USP between 2012 and 2015, specialist in shoulder and elbow surgery from USP in 2016. Also, may be part of the project and participate in surgeries the residents of shoulder and elbow surgery from Hospital Alvorada Moema, as well as the residents of Orthopedics and Traumatology at this hospital. In addition, residents in shoulder and elbow surgery at Albert Einstein Hospital will participate in the study.

As with patient randomization, surgeons will be randomized; it will be done by computer software (<http://www.randomizer.org>), where each surgeon will be assigned a number from 1 to 5. This will be attached to the patient's envelope and the responsible surgeon will be revealed prior to the intervention, immediately after application of anesthetic technique.

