## Statistical Planning

Descriptive analyzes of variables will be based on absolute frequencies and percentages for categorical variables and summary measures as means and standard deviations or medians and quartiles, as well as minimum and maximum values for numerical variables (37). Clinical scores will be represented by individual profile graphs separately by surgical technique group.

The groups will be compared for the presence of categorical clinical outcomes (failures, complications and healing integrity) by Chi-square or Fisher's exact tests, depending on the distribution observed after data collection.

For inferential analysis of numerical clinical outcomes, mixed models will be used and, if the normal distribution is not adequate, generalized mixed models will be used (38). The models will have time effects (preoperative, 6, 24 and 48 weeks after intervention), surgical technique group (open repair or arthroscopic repair) and the interaction effect between time and group. The size of the lesion (smaller than three cm or larger than three cm) will also be included in the models as a control variable, seeking to avoid possible biases.

The analyzes will be performed with the aid of the SPSS program (39), considering a significance level of 5%.

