## Sample Size Estimate

The sample size estimate was obtained to detect differences between the open and arthroscopic repair groups in relation to the primary outcome of the study, Constant-Murley Score (CM) instrument after the intervention.

Kukkonen's et. al study (40) estimated the clinically important minimal difference in CM score in 10.4 points in patients with rotator cuff rupture after three months of surgical treatment by the arthroscopic method.

The estimated sample size of 45 patients per group, 90 patients in total, would reach 90% power to detect a 10.4 point difference between groups in the CM instrument postoperative score with standard deviation of up to 15 points with significance level of 5% using a t-Student test. Predicting a loss of around 10% at 12 months of follow-up, we aimed to recruit 50 patients in each group.

The sample size estimate calculations were performed with the aid of the PASS software (41).

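### Allocation is described as one list over two hospitals with no stated stratification, and neither costs nor QALYs are adjusted for hospital or tear size, which loses precision in the incremental cost and the ICER.

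*Combined protocol and SAP*

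**What the plan says.** Study Design states "This project will be a multicenter randomized clinical trial". The Participants section names two recruiting sites, a shoulder and elbow referral centre and a municipal hospital, and adds "Both hospitals will be co-participants in the project in question".

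Allocation and Randomization says "Patients will be consecutively allocated to one of two proposed treatment methods", using "opaque and sealed envelopes that will be numbered according to the computer generated randomization list". The list is in the singular. The section gives no allocation ratio, block size, stratum or per-hospital list. The Team section adds a second random sequence over five surgeons ("As with patient randomization, surgeons will be randomized"), and the surgeon's number is attached to the patient's envelope.

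The Sample Size Estimate section says "we aimed to recruit 50 patients in each group".

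For the clinical scores, Statistical Planning lists time, technique group and their interaction, and continues: "The size of the lesion (smaller than three cm or larger than three cm) will also be included in the models as a control variable". Hospital is not among the terms. The Economic analysis section specifies a decision tree, direct and indirect costs, utilities, QALYs, an ICER and a sensitivity analysis. It describes no adjustment for hospital or tear size.

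**The concern.** The trial's stated goal is the cost-effectiveness ratio. A referral centre and a municipal hospital may well have different costs per patient, and larger tears may cost more to repair. If hospital is not balanced by design, its mix can differ between arms by chance. Arm-average costs fed into a decision tree carry that difference directly into the incremental cost: the shift equals the difference in hospital share times the cost gap between hospitals.

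The plan accepts that case mix matters, since it adjusts the clinical models for tear size. It describes no such protection for the analysis that answers its main question, and hospital is handled nowhere. At stake is the precision of the incremental cost and the ICER in a trial of 100 patients.

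**Working it through.** **1. The plan's sample size.** Inputs from Sample Size Estimate: difference 10.4, SD 15, significance level 5% (two-sided assumed), power 90%.

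- Normal approximation: n = 2 × (1.960 + 1.282)² × 15² / 10.4² = 43.7, so 44 per arm.
- Student t-test: n = 44.7, so 45 per arm, with power 90.2%. This reproduces the plan.
- Allowance for 10% loss: 45 / 0.9 = 50 per arm. This also reproduces.

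**2. Do unequal arms matter for Constant-Murley?** If the list were simple 1:1 randomisation of 100 patients, arms of exactly 50/50 would occur in 8.0% of lists, and a smaller arm of 45 or fewer in 36.8%. Power of the t-test after 10% loss:

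| Arms randomised | Power |
|---|---|
| 50/50 | 90.2% |
| 45/55 | 89.9% |
| 40/60 | 89.0% |

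The loss is about 1 percentage point at 40/60, so it is negligible.

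**3. How far can hospital mix differ between arms?** Let p be one hospital's share of the 100 patients (assumed, since the documents do not give it). With totals fixed at 50/50, the SD of the between-arm difference in share is √[p(1−p) × (1/50 + 1/50) × 100/99]. At p = 0.5 this is √(0.25 × 0.04 × 1.0101) = 0.1005, or about 10 points. The tail chances are hypergeometric for fixed totals and simulated for a simple list.

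| Assumed hospital split | SD, points (fixed totals / simple) | 10 points or more (fixed / simple) | 20 points or more (fixed / simple) |
|---|---|---|---|
| 50/50 | 10.1 / 10.1 | 31.7% / 36.8% | 7.1% / 5.7% |
| 70/30 | 9.2 / 9.3 | 27.5% / 28.7% | 4.9% / 3.1% |
| 80/20 | 8.0 / 8.1 | 21.1% / 21.4% | 2.3% / 1.4% |

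Fixing the arm totals does not balance the hospitals. The same figures apply to any two-level factor, including tear size at 3 cm.

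**4. What this does to the incremental cost.** Let G be the cost gap between hospitals and s the within-hospital cost SD. The documents give neither, so the result is expressed in G/s.

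- Balanced and adjusted: variance = s² × (1/50 + 1/50) = 0.04 s².
- Unadjusted: variance = 0.04 × [s² + p(1−p)G²].
- Ratio = 1 + p(1−p)(G/s)².

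| G/s (assumed) | Ratio at 50/50 | Ratio at 70/30 | Ratio at 80/20 |
|---|---|---|---|
| 0.5 | 1.06 | 1.05 | 1.04 |
| 1 | 1.25 | 1.21 | 1.16 |
| 2 | 2.00 | 1.84 | 1.64 |

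For the cost question at an even split and G = s, 1/1.25 = 0.80, which is like using 80 of the 100 patients. In standard errors, the three even-split ratios are increases of about 3% (√1.0625 = 1.031), 12% (√1.25 = 1.118) and 41% (√2 = 1.414).

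**5. How much can adjustment alone recover?** With equal arms and equal hospitals, the correlation between arm and hospital equals the difference in share, d. The adjusted variance is then multiplied by 1/(1−d²): 1/(1−0.01) = 1.01 at d = 10 points and 1/(1−0.04) = 1.04 at 20 points. Adjustment therefore recovers nearly all of the loss, even if the list cannot be changed.

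**The case against.** The strongest reply has four parts.

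- **Silence is not absence.** The protocol does not say that blocks or strata are not used, and the aim of 50 per group fits a list with fixed totals. This stands. A reader might infer that the trial uses unrestricted simple randomisation; the text does not establish that. The hospital-mix result survives, because it is much the same for fixed totals.
- **This is not bias.** Randomisation keeps the expected incremental cost correct, and an ordinary unadjusted standard error already reflects between-hospital variation. This stands in full. A reader might infer that the ICER would be systematically distorted; it would not. What is lost is precision.
- **The cost gap is unknown.** The documents give no gap and do not say whether costs are hospital-specific or standard unit costs. Common unit costs could remove much of it, and at G = 0.5s the loss is small. This stands, so no figure in currency is given. The Economic analysis section does mention a sensitivity analysis and other health-system scenarios, but neither is described as an adjustment for hospital mix in the trial data.
- **Stratifying by both hospital and tear size goes further than needed.** Four strata among 100 patients may leave incomplete blocks, and each envelope also carries a surgeon number. This stands; hospital alone is enough for the design, with tear size handled in the analysis.

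**Conclusion.** The point holds as a limited but real weakness. As described, the allocation does not balance the two hospitals. The clinical models omit hospital, and the economic analysis adjusts for neither hospital nor tear size. If the list is simple or restricted only on totals, and the hospitals recruit equally, the difference in hospital share has an SD of about 10 points and reaches 10 points in 32% to 37% of lists. The price is a variance of the unadjusted incremental cost about 1.06, 1.25 or 2.0 times what it could be, for an assumed gap of 0.5, 1 or 2 within-hospital SDs. If the true gap is small, so is the loss.

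A reader might also infer that the trial is underpowered because 50 per arm is not secured by the allocation rule. The figures do not support this: Constant-Murley power is still 89.0% at 40/60.

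**What to change.** 1. **If recruitment is not complete**, replace the single list in Allocation and Randomization with one permuted-block list per hospital, with random block sizes. Give each hospital its own numbered envelope series, and rebuild the surgeon sequence in the Team section to match. State the ratio and method.
2. **In any case**, add hospital to the mixed models in Statistical Planning. Estimate the incremental cost and QALY inputs to the Economic analysis with adjustment for hospital and tear size (3 cm cut).

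The cost is a second envelope and surgeon series, new wording in the plan, and slightly more analysis work. The sample size does not change. With blocks of 4 (assumed for illustration) and two hospitals, the arms could differ by at most 2 × 2 = 4 patients, that is 52/48. If recruitment has closed, the second step remains available, together with reporting how the sequence was in fact generated.
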